## Outcome

The outcome of the adverse event should be classified according to the following definitions:

- Recovered / resolved: the event has resolved (no further symptoms are present and no treatment is being received by the subject).
- Recovered / resolved with sequelae: the event has resolved but there may be lingering effects present (e.g., a scar following a cut or abrasion).
- Fatal: the subject died as a result of the event. This code should only be used for the event that caused the death, not any event that was present at the time of the subject's death. Fatal events require immediately reporting to the Sponsor (or an authorized representative).
- Unknown: may only be used in the event that the subject is lost to follow-up and no reliable data can be obtained.

### 11.2.3. AE reporting

All of AE will be reported to the Institutional Review Board of Tam Anh TP. Ho Chi Minh General hospital and Ethical Committee for Biomedical Research on Human Subjects of Vietnamese Ministry of Health in periodic reports.

### 11.2.4. AE follow-up

All AEs occurring during the Studystudy are to be followed up in accordance with good medical practice until resolved or judged no longer clinically significant, or if a chronic condition, until fully characterized. All follow-up results are to be reported to the Institutional Review Board of Tam Anh TP. Ho Chi Minh General hospital.

## 11.3. Serious Adverse Events

### 11.3.1. Definition

A serious adverse event (SAE) is any untoward medical occurrence or effect, at any dose, that:

- results in death;
- is life threatening (at the time of the event);
- requires hospitalization or prolongation of existing inpatients' hospitalization;
- results in persistent or significant disability or incapacity;
- is a congenital anomaly or birth defect;
- is considered an important medical event (an event that may not be immediately life- threatening or result in death or hospitalization, but based on medical judgment may jeopardize the subject and may require medical or surgical intervention to prevent any of the outcomes listed above (i.e., death of subject, life-threatening, hospitalization, prolongation of hospitalization, congenital anomaly, or persistent or significant disability/incapacity).

### 11.3.2. Reporting SAE

Any SAE, whether or not related to the study drug, must be reported immediately (within 24 hours of the investigator's awareness of the event) by telephone or email to Institutional Review Board of Tam Anh TP. Ho Chi Minh General hospital . Pregnancy in a study subject is not considered an adverse event. Serious complication of pregnancy are considered as a SAE.

Fatal or life-threatening SAEs must be reported urgently within 07 workdays of investigator's awareness of the event. Other SAEs must be reported within 15 workdays. The reports will be sent to Agency of Science, Technology and Training, Ethical Committee for Biomedical Research on Human Subjects of Vietnamese Ministry of Health and National centre of Drug information and adverse drug reactions monitoring (National DI and ADR center).

Investigator shall report adverse events that occur during the course of the Study directly to the competent regulatory authorities as required by and in accordance with the Applicable Law

## **12. STATISTICAL CONSIDERATIONS**

### **12.1. Sample size determination**

The ongoing pregnancy rate of patients in ART center – Tam Anh HCM hospital was 45.0% in the Antagonist IVF stimulation group. To show or refute that hypothesis: no significant difference in ongoing pregnancy rates when using DPOS protocol (40 - 42%) (43–45), we need 657 patients to produce a two-sided 95% confidence interval for the difference in population proportions with a width that is equal to 5% (margin = 5.0%, alpha = 5.0% and power = 80%). Considering a 10% loss to follow-up and protocol violation we plan to recruit 730 participants (365 per arm).

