stimulation cycle, the fresh oocytes and all thawed oocytes will be fertilized by ICSI. The freeze-all strategy will be applied in both arms, and single blastocyst frozen embryo transfer will be performed in the next menstrual cycle.

The ongoing pregnancy rate of patients in IVFTA HCM was 45.0% in the Antagonist IVF stimulation group. To show or refute that hypothesis: no significant difference in ongoing pregnancy rates when using DPOS protocol (40 - 42%), we need 657 patients to produce a two-sided 95% confidence interval for the difference in population proportions with a width that is equal to 5% (margin = 5.0%, alpha = 5.0% and power = 80%). Considering a 10% loss to follow-up and protocol violation, we plan to recruit 730 participants (365 per arm). The primary endpoint is the ongoing pregnancy rate after the first completed transfer. Secondary endpoints are ovarian stimulation, embryo culture characteristics, drop-out rate, and DPOS and GnRH antagonist protocol safety.

All analyses will be performed on an intention-to-treat basis using the R statistical package

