### **12.3. Statistical analyses**

Statistical analysis will be conducted according to the ITT principle, in which all randomized women will be conducted for the comparison of primary outcomes between treatment groups. The per-protocol analysis may be conducted, but these results would be considered reference only. All tests will be two-tailed, and differences with p-value < 0.05 will be considered statistically significant. The statistical software used was R, version 4.0.5 (R Foundation for Statistical Computing). We will develop a detailed statistical analysis plan that will be completed before data-lock.

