#### *12.3.2. Primary outcome*

The primary outcome, ongoing pregnancy rate will be compared using Pearson's chi-square test or Fisher's exact test for unadjusted analysis. We will also compute the unadjusted risk ratio (RR) and its 95% confidence interval (95% CI). In the event of a prominent imbalance of potential confounders between arms, we will perform multivariable Log-Binomial or Poisson Regression with a robust variance estimate to compute adjusted RR and its 95% CI.

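### The hypothesis and sizing sentence in 12.1 (repeated in 2.1) promises a 5% interval width, a 5% margin and 80% power that the design does not deliver and the planned analysis does not use

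*Protocol*

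**What the plan says.** **Hypothesis and size.** Section 12.1 takes a 45.0% ongoing pregnancy rate on the antagonist protocol from the centre's own experience and states the aim as "To show or refute that hypothesis: no significant difference in ongoing pregnancy rates when using DPOS protocol (40 - 42"%). Section 2.1 repeats the sentence: "we need 657 patients to produce a two-sided 95% confidence interval for the difference in population proportions", continuing "with a width that is equal to 5% (margin = 5.0%, alpha = 5.0% and power = 80"%). After an allowance of 10% for loss and protocol violation, 657 becomes 730, or 365 per arm.

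**Analysis.** Section 12.3 is by intention to treat, "in which all randomized women will be conducted for the comparison of primary outcomes between treatment groups". On sidedness it says "All tests will be two-tailed, and differences with p-value" below 0.05 counting as significant. In 12.3.2, "The primary outcome, ongoing pregnancy rate will be compared using" a Pearson chi-square or Fisher exact test, and then "We will also compute the unadjusted risk ratio (RR) and its 95% confidence interval (95% CI"). An adjusted risk ratio follows if potential confounders are clearly imbalanced. The interim look in 12.3.6 is also a two-sided significance test.

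**Objective and design.** Sections 4.1 and 5 speak only of comparing the two protocols. Non-inferiority and equivalence are not named anywhere.

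**Later detail.** Section 12.3 adds: "We will develop a detailed statistical analysis plan that will be completed before data-lock".

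**The concern.** Three things in the sizing sentence do not fit together or do not fit the analysis.

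- A CI width and a margin are different design quantities, yet one 5% serves as both. A power is also attached to what is worded as a precision target.
- The sentence aims at showing or refuting the absence of a difference. A two-sided test of equality can only do the refuting.
- The sizing quantity is a CI for the difference in proportions. The analysis section reports a risk ratio, and nothing says what any interval has to exclude.

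What is at stake is how a non-significant result will be read. Section 2.1 already describes DPOS as easier to use and cheaper, so a report of no significant difference would be taken as support for switching. At the protocol's own assumed rates, a non-significant result is the likely outcome, and it would usually leave open a loss larger than the protocol's own 5 points.

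**Working it through.** **Inputs (12.1, 12.2, 12.3).** Control rate 45%; DPOS 40% to 42%, with 45% added for true equality; two-sided alpha 5%; 1:1 allocation. n = 365 per arm is all randomised patients. n = 329 per arm is 657/2 rounded up, after the 10% loss. DPOS minus antagonist throughout.

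**1. The plan's own figure.** The loss step reproduces: 657 / 0.90 = 730. The 657 does not follow from any of three readings of the 5%. With v = 0.45 x 0.55 + p(1 - p), v runs from 0.4875 (p = 0.40) to 0.495 (p = 0.45).

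| Reading of 5% | Formula, n per arm | Result |
|---|---|---|
| Full CI width 5 points | 1.96² x v / 0.025² | 2,997 to 3,043 |
| CI half-width 5 points | 1.96² x v / 0.05² | 750 to 761 |
| Margin 5 points, 80% power at equality | (1.960 + 0.842)² x 0.495 / 0.05² | 1,555 |

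The plan has 329 per arm. So the number does not tell the reader which meaning was intended.

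**2. Precision delivered.** Half-width = 1.96 x sqrt(v / n).

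- n = 365: 1.96 x sqrt(0.495 / 365) = 0.0722, full width 14.4 points.
- n = 329: 1.96 x sqrt(0.495 / 329) = 0.0760, full width 15.2 points.

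**3. Power of the planned test at 365 per arm.** s0 is the pooled and s1 the unpooled standard error; power is about Phi((d - 1.96 s0) / s1) plus a small opposite tail.

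- 45% v 40%: (0.05 - 0.0717) / 0.0365 = -0.59, power 0.277. Exact binomial enumeration gives 1 - 0.728 = 0.272.
- 45% v 42%: (0.03 - 0.0719) / 0.0367 = -1.14, power 0.129. Exact: 1 - 0.874 = 0.126.
- With 329 per arm: about 25% and 12%.

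**4. What a non-significant result would leave open.** Exact enumeration over all pairs of counts, n = 365, uncorrected chi-square test, Newcombe 95% CI.

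| True DPOS rate | P(p >= 0.05) | P(p >= 0.05 and lower limit < -5 points) | Share of non-significant results |
|---|---|---|---|
| 45% | 0.951 | 0.701 | 74% |
| 42% | 0.874 | 0.795 | 91% |
| 40% | 0.728 | 0.702 | 96% |

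At 329 per arm the shares are 76%, 92% and 97%.

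**5. Examples at 365 per arm.**

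| DPOS v antagonist | p | Difference, points (95% CI) | RR (95% CI) |
|---|---|---|---|
| 164 v 164 | 1.00 | 0 (-7.2 to 7.2) | 1.00 (0.85 to 1.17) |
| 153 v 164 | 0.41 | -3.0 (-10.1 to 4.2) | 0.93 (0.79 to 1.10) |
| 146 v 164 | 0.18 | -4.9 (-12.0 to 2.2) | 0.89 (0.75 to 1.05) |
| 138 v 164 | 0.051 | -7.1 (-14.2 to 0.0) | 0.84 (0.71 to 1.00) |

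Even identical counts leave a 7-point loss open.

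**6. If 5 points were a margin.** P(lower limit > -5 points) = Phi((0.05 - d) / s1 - 1.96), with d the true deficit, at n = 365: 0.274 at equality, 0.079 at DPOS 42%, 0.025 at 40%. At 40% the assumed deficit equals the margin.

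**The case against.** **It may only be a clumsy null hypothesis.** Read that way, the two-tailed test in 12.3 and the chi-square or Fisher test in 12.3.2 match it, and only the verb is loose. This partly stands: the planned test is valid for a two-sided comparison, and no wrong decision rule is written. But a plain null hypothesis has no use for a 5% margin, and this reading does not rescue the stated width and power.

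**12.1 does name the right quantity.** It does specify a CI for the difference in proportions, so the protocol is not silent on that scale. The defect is that 12.3.2 does not take it up and the role of the 5% is never stated. The arm counts behind the risk ratio also yield the difference directly.

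**The SAP can settle it.** A risk difference and the choice of interval method could well be left there. The sizing sentence could not: its width, margin and power are protocol statements. The SAP is due only before data-lock, whereas the interim look at 366 patients assesses efficacy and futility.

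**Stronger readings that a reader might infer.**
- *That the protocol treats p >= 0.05 as proof of no difference.* It says no such thing.
- *That this is a non-inferiority or equivalence trial analysed with the wrong test.* Sections 4.1, 5, 12.3 and 12.3.6 all describe a two-sided comparison, and one ambiguous word in 12.1 does not outweigh them.

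**Conclusion.** The point holds as an internal inconsistency combined with stated figures that the design does not meet. It should be fixed, but it does not invalidate the planned test. The 5% width is in fact about 14 to 15 points. The 80% power is about 27% (45% v 40%) or 13% (45% v 42%) with all 365 per arm analysed. At 365 per arm, between 74% and 96% of non-significant results would be compatible with a loss of more than 5 points, over true DPOS rates from 45% down to 40%.

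These figures rest on the 45% control rate in 12.1 and on every randomised woman being analysed. Section 7.2 excludes some protocol violators, so 365 per arm is the maximum; the 329-per-arm figures are slightly less favourable. The shares in step 4 depend little on the interval method.

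It would be tempting to conclude that 730 patients are too few. That is a separate question and is not argued here: the point is that the text should state what 730 patients can give.

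**What to change.** 1. **Section 12.3.2.** Keep the test and the risk ratio. Add the risk difference (DPOS minus antagonist) with a two-sided 95% CI, for example Newcombe.
2. **Sections 2.1 and 12.1.** State a two-sided comparison. Delete the hypothesis of no significant difference, the 5% width and margin, the 80% power claim, and the statement that 657 patients are needed to achieve them. Keep 730 as planned enrolment. State the CI half-width (about 7.2 points at 365 per arm, 7.6 at 329) and the power given in the working. Add that a non-significant result will be reported as the CI and not as showing no difference or similarity.
3. **Only if** the sponsor can document that 5 points was a margin fixed before any outcome data by arm were seen: state that absence of a relevant loss is claimed only if the lower 95% limit exceeds -5 points, and disclose that the planned size gives about a 27% chance of this at true equality, 8% at a DPOS rate of 42% and 2.5% at 40%.

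**Timing.** Amend before anyone deciding sees outcome data by arm. The summary of changes reports 272 recruited by August 2024, and the document does not say whether the interim at 366 patients has taken place. If it has, record who has seen what.

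**Cost.** A wording amendment with IRB review (section 1), less favourable figures on the page, and no claim of no difference unless item 3 applies. Under item 3 an inconclusive result is likely, about 73% even at true equality. Enrolment, visits, analysis set and primary test do not change, and no new data are needed.

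### 657 evaluable women give a 95% confidence interval about 15 points wide, not 5, and about 25% power at best, not 80%, for a 5-point difference or margin

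*Protocol*

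**What the plan says.** Section 12.1 starts from an ongoing pregnancy rate that "was 45.0% in the Antagonist IVF stimulation group" at the Ho Chi Minh City centre and assumes 40–42% under DPOS. The stated aim is "To show or refute that hypothesis: no significant difference in ongoing pregnancy rates when using DPOS protocol (40 - 42"%). It then says the trial needs "657 patients to produce a two-sided 95% confidence interval for the difference in population proportions with a width that is equal to 5"%. In section 2.1 the parameters in brackets read "margin = 5.0%, alpha = 5.0% and power = 80"%, and section 12.1 gives the same ones.

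The allowance for losses follows: "Considering a 10% loss to follow-up and protocol violation we plan to recruit 730 participants (365 per arm"). Sections 12.3 and 12.3.2 plan two-tailed tests at 0.05 with a chi-square or Fisher's exact test and a risk ratio. No section declares a non-inferiority or equivalence design, and the protocol does not say what kind of margin the 5% is.

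**The concern.** A few hundred women per arm cannot estimate a difference between rates near 45% to within a 5-point-wide interval. The sentence also mixes two bases for a sample size, the width of an interval and the power of a test. A precision calculation needs no power, and a power calculation needs a stated difference or margin.

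What is at stake is how a null result will be read. The aim is worded as showing or refuting no significant difference, and the test is two-tailed. If power is low, non-significance is the likely outcome even when DPOS is truly 3 to 5 points worse. A reader who trusts section 12.1 would take that as evidence of similarity backed by 5-point precision and 80% power. The ethics board approved 730 on these figures, and the DSMB's efficacy and futility review after 366 women (12.3.6) has the same figures as its background.

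**Working it through.** **Inputs (section 12.1).** Antagonist 45%; DPOS 40–42% (45% added as the equal-rates case); 657 evaluable in total; 10% loss; 730 randomised 1:1.

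**The plan's own figures.** The loss step reproduces: 657 / 0.9 = 730, or 365 per arm. So 657 is a total, 328.5 per arm, taken as 329 below. The 657 itself does not follow from the stated inputs.

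**Interval width.** SE = √[0.45 × 0.55/n + p(1 − p)/n], where p is the DPOS rate; half-width = 1.96 × SE.

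| DPOS rate | SE, n = 329 | Half-width, n = 329 | Full width, n = 329 | Half-width, n = 365 |
|---|---|---|---|---|
| 40% | 0.0385 | 7.5 points | 15.1 | 7.2 |
| 42% | 0.0386 | 7.6 points | 15.1 | 7.2 |
| 45% | 0.0388 | 7.6 points | 15.2 | 7.2 |

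Solving for n = 1.96² × [0.2475 + p(1 − p)] / h²:
- Full width 5 (h = 0.025): about 2,996 to 3,042 per arm.
- Half-width 5 (h = 0.05): about 749 to 761 per arm.

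Neither reading of width fits 329 or 365 per arm.

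**Power if the 5% is a difference to detect.** Two-sided 5% test, pooled SE under the null, n = 329:
- 45% v 40%: Φ[(0.05 − 1.96 × 0.03854)/0.03849] = Φ(−0.66) = 0.25.
- 45% v 42%: Φ[(0.03 − 1.96 × 0.03865)/0.03864] = Φ(−1.18) = 0.118; adding the opposite tail gives 0.121.

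80% power for 45% v 40% needs about 1,534 per arm.

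**Power if the 5% is a non-inferiority margin.** One-sided 2.5%, n = 329; power = Φ[(0.05 − (0.45 − p))/SE − 1.96]:
- p = 45%: Φ(0.05/0.03879 − 1.96) = Φ(−0.67) = 0.25 (0.36 at one-sided 5%).
- p = 42%: Φ(0.02/0.03864 − 1.96) = Φ(−1.44) = 0.075.
- p = 40%: the true deficit equals the margin, so power is 0.025 at any sample size.

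With equal rates, 80% power needs about 1,555 per arm.

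**If 657 were per arm.** This contradicts 365 per arm, and the half-width would still be 5.3 to 5.4 points. Power would be 45% for 45% v 40%, and 45% for non-inferiority with equal rates (57% at one-sided 5%).

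**What 329 per arm does give at 80% power.**
- Superiority: a fall from 45% to 34.3%, or 10.7 points (computed power 0.80).
- Non-inferiority with equal 45% rates: a margin of (1.96 + 0.8416) × 0.03879 = 10.9 points.

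**A possible origin.** An 80% interval of half-width 5 points with 50% in each arm needs 2 × 1.2816² × 0.5 / 0.05² = 657.0 in total. The 80% meant as power may have been entered as the confidence level. This is a guess, and nothing above depends on it.

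**The case against.** The strongest reply is that the protocol never claims non-inferiority. The word margin stands in brackets straight after the statement about width, so it may mean margin of error. In that case the non-inferiority powers, and the remark that an assumed deficit of 3 to 5 points uses up a 5-point margin, do not apply. This is fair, and those results are conditional on that reading. It does not save the figures: a margin of error of 5 points needs about 750 per arm.

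Second, the main analysis is by intention to treat, and women with no blastocyst to transfer count as failures (section 8). The denominator may therefore be closer to 365 than 329 per arm, although section 7.2 excludes some protocol violators. The half-width then becomes 7.2 points and power for 45% versus 40% rises from 25% to 28%, which leaves the conclusion unchanged.

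Third, the planned test and risk ratio remain valid, and the reported interval will show the precision actually achieved. This too is right. The damage is to the justification of the sample size and to the reading of a null result, not to estimation.

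Finally, the protocol leaves analysis detail to a later analysis plan, but it states these sample-size figures itself, twice, so they cannot be treated as deferred.

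**Conclusion.** The concern holds. At the protocol's own rates the 95% interval is about three times as wide as stated (15 points against 5). Even reading width as half-width, it is 7.6 points against 5, or 7.2 with no losses. Power for 45% versus 40% is 25%, and for 45% versus 42% it is 12%, against the stated 80%. If the 5% is a non-inferiority margin, power at one-sided 2.5% runs from 25% with equal rates down to 2.5% at a DPOS rate of 40%.

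These results rest on the usual large-sample formulas for two independent proportions, 1:1 allocation and the rates in section 12.1. Approximation or rounding cannot account for gaps of this size. The correction is necessary because the interpretation of the primary result depends on these figures.

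**What to change.** Keep 730 and amend sections 12.1 and 2.1 together. Make precision the single basis, and remove both the 5% width and the 80% power attached to a 5% margin. Suggested text:

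> The trial will estimate the difference in ongoing pregnancy rate between DPOS and GnRH antagonist. With 657 evaluable women (about 329 per arm) and rates of 40–45%, the two-sided 95% confidence interval will extend about 7.6 points either side of the estimate (about 7.2 points with all 730). For reference, a two-sided 5% test on 657 women has 80% power for a fall of about 10.7 points from 45%. A non-significant result will not be taken as evidence that the protocols are equivalent.

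This also replaces the aim of showing or refuting no significant difference. Section 12.3.2 should report the difference in rates with its 95% interval beside the risk ratio, so that the stated precision refers to something the trial reports.

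If the sponsor does intend a 5-point non-inferiority margin, the protocol must say so. It should then state that power is about 25% with equal rates (one-sided 2.5%) and that 80% would need about 1,555 per arm.

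The cost is a text amendment, which needs ethics board approval under section 1. It adds no patients and changes no procedure. The stated precision and power become less favourable, and the 10.7 points describes what 730 recruited can detect without showing that a difference of that size is the relevant one.

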### **12.2. Randomization**

After signed informed consent, patients will be randomly assigned in a 1:1 ratio to receive one protocol: Antagonist or DPOS. Randomization will be centrally controlled by a data scientist, who is not involved in any treatment procedure. When there is an eligible participant to be enrolled in the Study, clinicians from the specific site will enter the study data management center to get the allocation of patients according to a computer-generated randomization list in a 1:1 ratio, with a variable block size of 2, 4, 6 or 8. Apart from randomization, patients will be followed up and treated according to the protocol at each center.

